7 PROTOCOL SYNOPSIS

Study Title	A Phase 3 Randomized, Double-Blind, Multi-Center Study to Compare the Safety and Efficacy of Omadacycline IV/PO to Moxifloxacin IV/PO for Treating Adult Subjects with Community-Acquired Bacterial Pneumonia (CABP)
Clinical Phase	3
Study Rationale	
PTK 0796 (hereafter referred to as omadacycline) is the first member of the aminomethylcycline class of antibiotics, which are semi-synthetic derivatives of the tetracycline class. As a class, the tetracyclines have been in use for approximately 70 years. They are well-tolerated, and have proven effective in the treatment of a variety of bacterial infections.
 
Omadacycline was evaluated in a Phase 2 study of 219 subjects with complicated skin and skin structure infection (cSSSI) and a sponsor-terminated Phase 3 study that enrolled 143 subjects with cSSSI. Omadacycline was well-tolerated and demonstrated efficacy similar to an established comparator (linezolid).
 
Omadacycline has been shown to have in vitro activity against the most common typical and atypical causes of CABP. Further, it has been shown to be effective in animal models of lower respiratory tract infections caused by Streptococcus pneumoniae and Haemophilus influenzae. It is expected that omadacycline will achieve levels in the lower respiratory tract comparable to related tetracyclines (doxycycline and tigecycline) which have been used to successfully treat subjects with CABP.
 
Omadacycline has demonstrated activity against the most common CABP pathogens, including isolates resistant to standards of care. This study is intended to evaluate the safety and efficacy of intravenous (iv) and oral (po) omadacycline as compared to iv and po moxifloxacin in the treatment of adults with CABP.

Study Objective(s)	
Primary objective:
 
The primary objective of this study is to demonstrate that omadacycline 100 mg iv every 12 hours (q12h) for 2 doses, followed by 100 mg iv/300 mg po once every 24 hours (q24h) is non-inferior to moxifloxacin 400 mg iv/po q24h in the treatment of adults with CABP.
 
Secondary objectives:
 
• To evaluate the safety of omadacycline in the treatment of adult subjects with CABP in the Safety population.• To evaluate the Clinical Response according to the identified causative pathogen.• To evaluate the pharmacokinetics (PK) of omadacycline in adult.

subjects with CABP.

Study Design	This is a randomized (1:1), active comparator-controlled, double-blind, Phase 3 study comparing omadacycline and moxifloxacin in the treatment of adults with CABP (Pneumonia Outcomes Research Team [PORT] Risk Class II, III, or IV). Both iv and po phases of the study will be double-blind. Enrollment of subjects with disease characterized as PORT Risk Class II will be limited to no more than 15% of randomized subjects. Enrollment of subjects who have received a single dose of an allowed short-acting antibiotic (see Appendix 1) within the 72 hours prior to the first dose of test article will be limited to no more than 25% of randomized subjects.
Approximate Duration of Subject Participation	Subjects will participate in the study for approximately 30 days. Following Screening, eligible subjects will be randomly assigned to receive 7 to 14 days of treatment with either omadacycline or moxifloxacin. A post therapy evaluation visit will occur approximately 5 to 10 days after the last dose of test article and a follow-up telephone contact will occur approximately 30 to 37 days after the first dose of test article.
Approximate Duration of Study	The study is expected to be clinically complete in approximately 18 months.
Approximate Number of Subjects	750 randomized subjects.
Approximate Number of Study Centers	150
Diagnosis and Main Criteria for Inclusion	
1. Written and signed informed consent must be obtained before any protocol specific assessment is performed.2. Male or female, age 18 years or older.3. Has at least 3 of the following symptoms:
• Cough• Production of purulent sputum• Dyspnea (shortness of breath)• Pleuritic chest pain4. Has at least TWO of the following abnormal vital signs:
• Fever or hypothermia documented by the investigator (temperature > 38.0°C [100.4°F] or < 36.0°C [95.5°F])• Hypotension with systolic blood pressure (SBP) < 90 mm Hg• Heart rate > 90 beats per minute (bpm)• Respiratory rate (RR) > 20 breaths/minute5. Has at least 1 clinical sign or laboratory finding associated with

CABP:

- Hypoxemia (partial pressure of arterial oxygen [PaO₂] < 60 mm Hg by arterial blood gas [ABG] or oxygen saturation < 90% by pulse oximetry)
- Physical examination findings of pulmonary consolidation (eg, dullness on percussion, bronchial breath sounds, or egophony)
- An elevated total white blood cell (WBC) count (> 12,000 cells/mm³) or leucopenia (WBC < 4,000 cells/mm³) **or** elevated immature neutrophils (> 15% band forms, see % bands calculation in [Appendix 4](#), regardless of total peripheral WBC count)
- 6. Radiographically-confirmed pneumonia, ie, new or progressive pulmonary infiltrate(s) on chest X-ray (CXR) or chest computed tomography (CT) scan consistent with acute bacterial pneumonia within 24 hours prior to the first dose of test article.
- 7. Has disease categorized as being PORT Risk Class II, III, or IV at Screening (see PORT Risk Class calculation in [Appendix 2](#)).
- 8. Is expected to require a minimum of at least 3 days of iv therapy for the initial treatment of CABP.
- 9. Females must have a negative urine pregnancy test at Screening and agree to comply with using an acceptable method of birth control as per your local requirements (eg, abstinence, po contraceptive, intrauterine device [IUD], barrier contraception [condom], tubal ligation, hysterectomy, bilateral oophorectomy, postmenopausal or vasectomized partner) from Screening through post therapy evaluation (PTE). Males must agree to use an acceptable method of birth control with female partner(s) and must not donate sperm from Screening through PTE.

Main Criteria for Exclusion

1. Has received 1 or more dose(s) of a potentially effective systemic antibacterial treatment within the 72 hours prior to the first dose of test article (a subject will be considered to have received a potentially effective systemic antibacterial treatment if the pathogen identified as causing infection is shown to be susceptible to the antibacterial given or, in the circumstance where a pathogen is not identified, if the antibacterial agent is approved for treatment of pneumonia or is known to have activity against any of the leading causes of CABP [eg, *Streptococcus pneumoniae*, *Haemophilus influenzae*, *Moraxella catarrhalis*, *Staphylococcus aureus*, *Legionella pneumophila*]). EXCEPTION: Subjects may be eligible despite prior antibacterial therapy if they have been treated with a single dose of a short-acting antibacterial (ie, an antibacterial whose standard dosing regimen is more frequent than once per day, see list in [Appendix 1](#)).
2. Is known or suspected to have CABP caused by a pathogen that may

be resistant to either test article (eg, *Klebsiella pneumoniae*, *Pseudomonas aeruginosa*, *Pneumocystis jiroveci*, obligate anaerobes, mycobacteria, fungal pathogens).

3. Suspected or confirmed empyema (a parapneumonic pleural effusion is not an exclusion criteria) or lung abscess.
4. Subjects with known or suspected hospital-acquired pneumonia (HAP) or healthcare-associated pneumonia (HCAP). HAP is defined as pneumonia with onset of clinical signs and symptoms \geq 48 hours after hospitalization in an acute in-subject health care facility. HCAP is defined as pneumonia acquired in a long-term care or subacute/intermediate healthcare facility (eg, nursing home) or in a subject admitted with pneumonia following a recent hospitalization (discharged within 90 days of current admission and previously hospitalized for \geq 48 hours).
5. Has known or is clinically suspected to have 1 or more of the following prior to randomization:
 - alanine aminotransferase (ALT) or aspartate aminotransferase (AST) $\geq 2 \times$ Upper Limit of Normal (ULN),
 - total bilirubin $> 1.5 \times$ ULN, or
 - evidence of end-stage liver disease (eg, ascites, hepatic encephalopathy).
6. Has a known history of having experienced unstable cardiac disease (eg, unstable angina, myocardial infarction, acute congestive heart failure, unstable cardiac arrhythmia, etc.) within the 3 months prior to Screening.
7. Has a QT interval corrected for heart rate using Fridericia's formula (QTcF) > 450 msec (males) or > 470 msec (females), are known to have long QT syndrome, use drugs of potential proarrhythmic or QT prolonging effect, and/or present with tachyarrhythmia.
8. Requires any form of dialysis (eg, hemodialysis, peritoneal dialysis).
9. History or evidence of severe renal disease or has a calculated creatinine clearance (CrCl) of < 30 mL/minute, using the Cockcroft-Gault equation (see equation in [Appendix 4](#)).
10. Evidence of significant immunological disease determined by any of the following:
 - Current or anticipated neutropenia defined as < 500 neutrophils/ mm^3
 - Known infection with Human Immunodeficiency Virus (HIV) and a cluster of differentiation 4 (CD4) count that is unknown or documented to be < 200 cells/ mm^3 within the last year, or an Acquired Immune Deficiency Syndrome (AIDS)-defining illness

- The receipt of cancer chemotherapy, radiotherapy, or potent, non-corticosteroid immunosuppressant drugs (eg, cyclosporine, azathioprine, tacrolimus, immune-modulating monoclonal antibody therapy, etc.) within the past 3 months, or the receipt of corticosteroids equivalent to or greater than 40 mg of prednisone per day or for more than 14 days in the prior 30 days (see equivalent corticosteroid doses in [Appendix 4](#))

11. Requires acute pharmacologic intervention to stabilize blood pressure (BP) and/or adequate tissue perfusion, OR has evidence of septic shock defined by ALL of the following:

- Fever or hypothermia documented by the investigator (temperature $> 38.0^{\circ}\text{C}$ [100.4°F] or $< 36.0^{\circ}\text{C}$ [95.5°F])
- Heart rate > 90 beats/minute
- RR > 20 breaths/minute
- WBC $> 12,000$ cells/ mm^3 or $< 4,000$ cells/ mm^3 or $> 10\%$ immature (band) forms, see % bands calculation in Appendix 4, regardless of the total peripheral WBC count
- Hypotension with SBP < 90 mm Hg despite an iv fluid challenge of 20-30 cc/kg over a 30 minute period
- Perfusion abnormalities that may include, but are not limited to, lactic acidosis (blood lactate concentration ≥ 4 mmol/L), oliguria, or acute alteration in mental status.

12. Known or suspected primary or metastatic neoplastic lung disease, aspiration pneumonia, active tuberculosis, cystic fibrosis, bronchiectasis, bronchial obstruction (eg, post-obstructive pneumonia), chronic neurological disorder preventing clearance of pulmonary secretions, or severe chronic obstructive pulmonary disease (COPD).

13. Pregnant or nursing (breastfeeding) women.

14. Has a history of hypersensitivity or allergic reaction (eg, anaphylaxis, urticaria, other significant reaction) to any tetracycline (eg, minocycline, doxycycline or tigecycline) or to any fluoroquinolone antibiotic.

15. Has a history of pseudotumor cerebri, or prior (within 2 weeks prior to Screening) or planned concomitant use of isotretinoin.

16. Has a history of systemic lupus erythematosus or lupus-like syndrome.

17. Has current evidence of pancreatitis.

18. Has a history of a central nervous system disorder that may predispose to seizures or lower the seizure threshold.

19. Use of other investigational drugs within 5 half-lives or 30 days prior

to Screening, whichever is longer.

20. Has previously been treated with omadacycline or previously enrolled in this study.
21. Any planned medical intervention that might interfere with the ability to comply with the study requirements.
22. Has a life expectancy of less than or equal to 3 months or any concomitant condition that, in the opinion of the investigator, is likely to interfere with evaluation of the response of the infection under study, determination of adverse events (AEs), or completion of the expected course of treatment.

Prior and Concomitant Treatment	No systemic prior or concomitant antibacterial therapy is allowed, other than a single dose of a short-acting antibacterial (see Exclusion Criterion number 1 and Appendix 1), within the 72 hours prior to the first dose of test article. All other medications not prohibited by the protocol and considered necessary for the subject's welfare may be administered and/or continued under the supervision of the investigator.
Test Article(s)	Subjects will be randomized (1:1) to 1 of the following 2 treatment arms: 
• Omadacycline• Moxifloxacin
Dosage and Administration	
• Omadacycline 100 mg iv q12h for 2 doses followed by 100 mg iv q24h (starting 24 h after first dose), with the option to switch to 300 mg po q24h after a minimum of 3 days (4 doses) of iv treatment.• Moxifloxacin 400 mg iv q24h (with a single placebo infusion to match the omadacycline dosing regimen 12 hours after the first dose on Day 1) with the option to switch to 400 mg po q24h after a minimum of 3 days (4 doses) of iv treatment.
Safety Evaluation	
• Physical exams• AEs and SAEs• Vital signs• Laboratory assessments• Electrocardiogram (ECG)• Pregnancy assessments
Efficacy Evaluation	
• In order to satisfy different health authority requirements, the primary variables assessing efficacy will be tested with 2 response endpoints:
❖ Successful Early Clinical Response (72-120 hours after first dose) will be determined programmatically and defined as survival with improvement in at least 2 of 4 subject symptoms (cough, sputum production, pleuritic chest pain,

dyspnea), as assessed by the investigator, without deterioration in any of these 4 symptoms.

- ❖ Successful Investigator's Assessment of Clinical Response at the PTE visit, defined as survival after completion of a test article regimen, with resolution of signs and symptoms of the infection to the extent that further antibacterial therapy is not necessary.
- Assessment of signs and symptoms of CABP by the investigator
- Microbiological assessment of the infection
- Assessment of clinical response

Health Outcomes Assessment	• Resource utilization
-----------------------------------	------------------------

Pharmacokinetics	• Population PK analysis
-------------------------	--------------------------

Statistical Analysis	
A number of subject populations have been defined for the various analyses of efficacy and safety, as follows:
 
• The intent-to-treat (ITT) population will consist of all randomized subjects.• The microbiological intent-to-treat (microITT) population will consist of subjects in the ITT population who have at least 1 causative pathogen identified at Screening from culture of a respiratory specimen (eg, respiratory fluid obtained by bronchoalveolar lavage or bronchoscopy; pleural fluid obtained by thoracentesis; or expectorated or induced sputum meeting adequacy criteria), culture of blood, or from a culture-independent method (eg, positive urinary antigen test for Streptococcus pneumoniae or Legionella pneumophila, or positive serology for Legionella pneumophila, Mycoplasma pneumoniae or Chlamydophila pneumoniae).• The clinically evaluable (CE) population will consist of all ITT subjects who received test article, have a qualifying CABP, an assessment of outcome, and meet all other evaluability criteria detailed in the Statistical Analysis Plan (SAP)• The microbiologically evaluable (ME) population will include subjects in the CE population who have at least 1 causative pathogen identified at Screening.• The Safety population will consist of all randomized subjects who receive test article.
-----------------------------	---

A 2-sided 95% confidence interval (CI) approach for the difference in the rate of early clinical success in the ITT population (primary analysis for the US FDA) will be used to test for non-inferiority (NI) of the

omadacycline arm compared to the moxifloxacin arm. For the primary analysis for the European Medicines Agency (EMA), 97.5% CIs for the difference in the rate of clinical success at PTE in the ITT and CE populations will be used to test for the NI of the omadacycline arm compared to the moxifloxacin arm.

Safety will be assessed through the use of summary statistics and clinical review of reported AEs, changes in vital signs, ECGs, and laboratory results obtained from blood samples taken during the study.

Data and Safety Monitoring Committee:

A Data and Safety Monitoring Committee (DSMC) (independent of the sponsor) will provide ongoing monitoring of safety data. Data will be provided to the DSMC as treatment A and treatment B.

Rationale for Number of Subjects	
The study is designed to show NI in the primary efficacy outcome of Early Clinical Response at 72-120 hours following the first dose of test article in the ITT population. An NI margin of 10% will be used for the analysis in the ITT population. The NI margin was based on an analysis of the historical data regarding the treatment effect of antibiotics in pneumonia.
 
The sample size determination is based on ensuring sufficient power for the secondary efficacy analyses of Investigator's Assessment of Clinical Response at PTE in the CE and ITT populations (co-primary efficacy outcomes for EMA) as well as the primary efficacy analysis of Early Clinical Response (efficacy outcome for FDA).
 
For the Investigator's Assessment of Clinical Response at PTE endpoint in the ITT population (PORT Risk Class III and IV) assuming an outcome rate of 79% in both treatment groups, NI margin of 10%, 80% power and a 1-sided alpha level of 0.0125 (since 1 CABP study is being conducted), using the sample size determination method of Farrington and Manning (Farrington and Manning, 1990), a total of 638 subjects (PORT Risk Class III and IV) are required. Assuming an 80% evaluability rate, 510 subjects will be available in the CE population. Assuming an 85% response rate in both treatment groups, a 10% NI margin, 1-sided alpha level of 0.0125, there is 81% power to show NI for Investigator's Assessment of Clinical Response at PTE in the CE population.
 
If 15% of enrolled subjects are assumed to have CABP of PORT Risk Class II, a total of 750 subjects are required. For the Early Clinical Response primary efficacy endpoint, with 750 subjects in the ITT population, a response rate of 79% for both treatment groups with a NI margin of 10%, a 1-sided alpha level of 0.025, there is a 92% power to show NI. Assuming the microbiological evaluability rate is 27%, a total of 202 subjects are expected to be in the microITT population.

---	--

Thus, 750 subjects provides sufficient power for the primary efficacy analyses for both the FDA and EMA regulatory authorities.

Ethical Considerations	This study will be conducted in accordance with applicable laws and regulations including, but not limited to, the International Conference on Harmonisation Guideline of Technical Requirements for Registration of Pharmaceuticals for Human use (ICH) Guideline for Good Clinical Practice (GCP) and the ethical principles that have their origins in the Declaration of Helsinki. The institutional review board (IRB)/independent ethics committee (IEC)/research ethics board (REB) must review and approve the protocol and informed consent form (ICF) before any subjects are enrolled. The subject must be consented using the approved ICF before any procedures specified in the protocol are performed.
-------------------------------	---

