12.1 Inclusion Criteria

To be eligible for randomization in this study, a subject must fulfill ALL of the following criteria:

1. Written and signed informed consent must be obtained before any protocol specific assessment is performed.
2. Male or female, aged 18 years or older
3. Has at least 3 of the following symptoms:
 - Cough
 - Production of purulent sputum
 - Dyspnea (shortness of breath)
 - Pleuritic chest pain.
4. Has at least TWO of the following abnormal vital signs
 - Fever or hypothermia documented by the investigator (temperature $> 38.0^{\circ}\text{C}$ [100.4°F] or $< 36.0^{\circ}\text{C}$ [95.5°F])
 - Hypotension with systolic blood pressure (SBP) < 90 mm Hg
 - Heart rate > 90 bpm
 - Respiratory rate (RR) > 20 breaths/minute.
5. Has at least 1 clinical sign or laboratory finding associated with CABP:
 - Hypoxemia (partial pressure of arterial oxygen [PaO_2] < 60 mm Hg by arterial blood gas [ABG] or oxygen saturation $< 90\%$ by pulse oximetry)
 - Physical examination findings of pulmonary consolidation (eg, dullness on percussion, bronchial breath sounds, or egophony)
 - An elevated total white blood cell (WBC) count ($> 12,000$ cells/ mm^3) *or* leucopenia ($\text{WBC} < 4,000$ cells/ mm^3) *or* elevated immature neutrophils ($> 15\%$ band forms, see % bands calculation in [Appendix 4](#), regardless of total peripheral WBC count).
6. Radiographically-confirmed pneumonia, ie, new or progressive pulmonary infiltrate(s) on chest X-ray (CXR) or chest computed tomography (CT) scan consistent with acute bacterial pneumonia within 24 hours prior to the first dose of test article.
7. Has disease categorized as being PORT Risk Class II, III, or IV at Screening (see PORT Risk Class calculation in [Appendix 2](#)).
8. Is expected to require a minimum of at least 3 days of iv therapy for the initial treatment of CABP.
9. Females must have a negative urine pregnancy test at Screening and agree to comply with using an acceptable method of birth control as per your local requirements (eg, abstinence, po contraceptive, intrauterine device [IUD], barrier contraception [condom], tubal ligation, hysterectomy, bilateral oophorectomy, postmenopausal or vasectomized partner) from Screening through post therapy evaluation (PTE). Males must agree to use an acceptable method of birth control with female partner(s) and must not donate sperm from Screening through PTE.

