7. Has a QT interval corrected for heart rate using Fridericia's formula (QTcF) $>$ 450 msec (males) or $>$ 470 msec (females), are known to have long QT syndrome, use drugs of potential proarrhythmic or QT prolonging effect and/or present with tachyarrhythmia.
8. Requires any form of dialysis (eg, hemodialysis, peritoneal dialysis).
9. History or evidence of severe renal disease or has a calculated creatinine clearance (CrCL) $<$ 30 mL/minute, using the Cockcroft-Gault equation (see equation in [Appendix 4](#)).
10. Evidence of significant immunologic disease determined by any of the following:
 - Current or anticipated neutropenia defined as $<$ 500 neutrophils/mm³
 - Known infection with human immunodeficiency virus (HIV) and a cluster of differentiation 4 (CD4) count that is unknown or documented to be $<$ 200 cells/mm³ within the last year, or an Acquired Immune Deficiency Syndrome (AIDS)-defining illness

- The receipt of cancer chemotherapy, radiotherapy, or potent, non-corticosteroid immunosuppressant drugs (eg, cyclosporine, azathioprine, tacrolimus, immune-modulating monoclonal antibody therapy, etc.) within the past 3 months, or the receipt of corticosteroids equivalent to or greater than 40 mg of prednisone per day or for more than 14 days in the prior 30 days (see equivalent corticosteroid doses in [Appendix 4](#)).

11. Requires acute pharmacologic intervention to stabilize blood pressure (BP) and/or adequate tissue perfusion, OR has evidence of septic shock, defined by ALL of the following:

- Fever or hypothermia documented by the investigator (temperature $> 38.0^{\circ}\text{C}$ [100.4°F] or $< 36.0^{\circ}\text{C}$ [95.5°F])
- Heart rate > 90 beats/minute
- RR > 20 breaths/minute
- WBC $> 12,000$ cells/ mm^3 or < 4000 cells/ mm^3 or $> 10\%$ immature [band] forms, see % bands calculation in [Appendix 4](#), regardless of the total peripheral WBC count
- Hypotension with SBP < 90 mm Hg despite an iv fluid challenge of 20-30 cc/kg over a 30 minute period
- Perfusion abnormalities that may include but are not limited to lactic acidosis (blood lactate concentration ≥ 4 mmol/L), oliguria, or acute alteration in mental status.

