Appendix 2: PORT Risk Class Calculation

Adapted from Fine, et al., 1997.

Subject Characteristic	Point Assignment
Age	
Male	Age (years)
Female	Age (years) -10
Nursing home resident ¹	+10
Coexisting illnesses	
Neoplastic disease ²	+30
Liver disease ³	+20
Congestive heart failure ⁴	+10
Cerebrovascular disease ⁵	+10
Renal disease ⁶	+10
Physical-examination findings	
Altered mental status ⁷	+20
Respiratory rate \geq 30/minute	+20
Systolic blood pressure < 90 mm Hg	+20
Temperature < 35°C (95°F) or \geq 40°C (104°F)	+15
Pulse \geq 125/minute	+10
Laboratory and radiographic findings	
Arterial pH < 7.35	+30
Blood urea nitrogen \geq 30 mg/dL (11 mmol/L) ⁶	+20
Sodium < 130 mmol/L	+20
Glucose \geq 250 mg/dL (14 mmol/L)	+10
Hematocrit < 30%	+10
Partial pressure of arterial oxygen < 60 mm Hg or oxygen saturation < 90% (by pulse oximetry)	+10
Pleural effusion	+10
PORT Score	Sum of numbers above

PORT Risk Class	PORT Score
I (ineligible for study)	0-50
II	51-70
III	71-90
IV	91-130
V (ineligible for study)	\geq 131

1. Subjects that reside in a nursing home or assisted living facility that provides 24-hour medical supervision are excluded from the study and should not be enrolled per Exclusion Criterion number 4.
2. Neoplastic disease is defined as any cancer, except basal or squamous cell cancer of the skin that was active at the time of presentation or diagnosed within one year of presentation. Subjects with neoplastic lung disease are excluded from the study and should not be enrolled per Exclusion Criterion number 12.
3. Liver disease is defined as a clinical or histologic diagnosis of cirrhosis or another form of chronic liver disease, such as chronic active hepatitis. Subjects with liver test abnormalities or evidence of end-stage liver disease as defined in Exclusion Criterion number 5 should not be enrolled.
4. Congestive heart failure is defined as systolic or diastolic ventricular dysfunction documented by history, physical examination, and chest radiograph, echocardiogram, multiple gated acquisition scan, or left ventriculogram. Subjects with acute congestive heart failure are excluded from the study and should not be enrolled per Exclusion Criterion number 6.
5. Cerebrovascular disease is defined as a clinical diagnosis of stroke or transient ischemic attack or stroke documented by magnetic resonance imaging or CT.

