6.1.4.1 Diagnosis of CABP

To be included in the CE-EOT and CE-PTE populations, subjects must meet the following protocol defined inclusion criteria that describe the CABP:

Inclusion Criterion 3: Has at least 3 of the following symptoms:

- Cough
- Production of purulent sputum
- Dyspnea (shortness of breath)
- Pleuritic chest pain.

Inclusion Criterion 4: Has at least 2 of the following abnormal vital signs:

- Fever or hypothermia documented by the investigator (po or rectal temperature $> 38.0^{\circ}\text{C}$ [100.4°F] or $< 36.0^{\circ}\text{C}$ [95.5°F])

- Hypotension with systolic blood pressure (SBP) < 90 mmHg
- Heart rate > 90 bpm
- Respiratory rate (RR) > 20 breaths/minute.

Inclusion Criterion 5: Has at least 1 clinical sign or laboratory finding associated with CABP:

- Hypoxemia Partial pressure of arterial oxygen (PaO₂) < 60 mmHg by arterial blood gas (ABG)
- Physical examination findings of pulmonary consolidation (dullness on percussion, bronchial breath sounds, egophony, rales, rhonchi, or decreased breath sounds)
- An elevated total white blood cell (WBC) count (> 12,000 cells/mm³) **or** leucopenia (WBC < 4,000 cells/mm³) **or** elevated immature neutrophils (> 15% band forms regardless of total peripheral WBC count).

Inclusion Criterion 6: Radiographically-confirmed pneumonia, ie, new or progressive pulmonary infiltrate(s) on chest X-ray (CXR) or chest computed tomography (CT) scan consistent with acute bacterial pneumonia within 24 hours prior to the first dose of test article.

If the imaging study is done more than 24 hours prior to the first dose of test article but within 48 hours, the subject will be included in the CE populations as long as the imaging study shows a new or progressive pulmonary infiltrate(s) consistent with acute bacterial pneumonia.

Inclusion Criterion 7: Have disease categorized as being PORT Risk Class II, III, or IV at Screening:

The Sponsor Medical Monitor will also review those subjects with a concomitant illness identified after baseline that could have presented at baseline as pneumonia. If it is determined that the subject does not have pneumonia but had another condition such as lung cancer at baseline, the subject will not be evaluable for the CE populations.

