Baseline assessments of clinical symptoms, clinical signs, abnormal vital signs, and abnormal laboratory signs of CABP will be presented for the ITT, Safety, microITT, and CE-PTE populations. The number and percentage of subjects with each of the CABP symptoms (cough, pleuritic chest pain, dyspnea, and phlegm/sputum production) by severity (absent, mild, moderate, severe) will be presented by treatment group. The number and percentage of subjects with the presence by severity (ie, absent, mild, moderate, severe) of the following clinical signs will be provided by treatment group: rales, rhonchi, dullness on percussion, bronchial breath sounds, wheezing, decreased breath sounds, and egophony. The number

and percentage of subjects with fever (defined as body temperature $> 38^{\circ}\text{C}$ [100.4°F] oral or rectal), hypothermia (defined as body temperature $< 36^{\circ}\text{C}$ [95.5°F] oral or rectal), hypotension with systolic blood pressure $< 90 \text{ mmHg}$, heart rate $> 90 \text{ bpm}$, respiratory rate $> 20 \text{ breaths/min}$, hypoxemia (defined as $\text{PaO}_2 < 60 \text{ mmHg}$ by arterial blood gas or oxygen saturation $< 90\%$ by pulse oximetry), elevated total WBC count ($> 12,000 \text{ cells/mm}^3$), leucopenia (WBC $< 4,000 \text{ cells/mm}^3$), elevated immature neutrophils ($> 15\%$ band forms regardless of total peripheral WBC count) and any of elevated total WBC count, leucopenia or elevated immature neutrophils will be summarized by treatment group. Differences between treatment groups will be tested for statistical significance using Fisher's exact test.

Risk factors for CABP will be presented by treatment group for the ITT, Safety, microITT, and CE-PTE populations. Risk factors include smoking (current, past, and descriptive statistics of the number of years since quitting for those subjects who were previous smokers), receipt of pneumococcal vaccine, prior lung infection, whether the subject had mild to moderate COPD, symptomatic asthma with wheezing, and chronic cough with or without sputum production. Differences between treatment groups will be tested for statistical significance using Fisher's exact test for categorical variables and the Wilcoxon rank sum test for continuous variables. Other medical and surgical history will be summarized based on MedDRA system organ class by treatment group for the ITT and Safety populations.

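### The hypothermia bound in Inclusion 4, Exclusion 11 and the SAP pairs 36.0°C with 95.5°F, but 36.0°C is 96.8°F, so the criterion carries two thresholds 0.72°C apart

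*Combined protocol and SAP*

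**What the plan says.** Inclusion Criterion 4 requires at least two of four abnormal vital signs: temperature, systolic blood pressure below 90 mm Hg, heart rate above 90, and respiratory rate above 20. The temperature item in the version 2.0 synopsis ends "or < 36.0°C [95.5°F". Section 12.1 repeats the pair in the item that opens "Fever or hypothermia documented by the investigator (temperature".

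Exclusion Criterion 11 uses the same pair, in the synopsis and in section 12.2. There, abnormal temperature is one of six items that must all be present: "OR has evidence of septic shock, defined by ALL of the following". Needing acute drug treatment to support blood pressure or perfusion is a separate route to the same exclusion.

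The SAP carries the pair in three places:
- 6.1.4.1, where Inclusion 4 is a condition for the CE populations ("Fever or hypothermia documented by the investigator (po or rectal temperature");
- 6.1.4.6, where Exclusion 11 removes subjects from the CE populations;
- 9.2, where the baseline tables count "hypothermia (defined as body temperature" below the same pair of values.

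Other SAP rules give 36°C alone: SIRS (6.3 and 9.2), modified ATS severity (9.2) and notable vital signs (Table 8).

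**The concern.** A two-unit threshold works only if both units describe the same temperature. Here they do not, so sites or programmers applying the figure in different units would classify the same subject differently.

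Three things depend on it:
- **Eligibility.** Inclusion 4 controls who is randomized.
- **CE membership and deviation reporting.** SAP 6.1.4.1 applies Inclusion 4 again for the CE populations. SAP 9.1 lists randomized subjects who failed a criterion, and SAP 13.1 has a deviation category for an unmet inclusion criterion.
- **Baseline description.** Within SAP 9.2, a subject at 35.5°C meets the SIRS temperature item but is hypothermic in the vital-sign summary only on the Celsius reading. The stabilization summary in SAP 10.4 also relies on absence of hypothermia and gives no figure of its own, so it may inherit the ambiguity.

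Neither figure is the cautious choice throughout. The Celsius bound lets more subjects satisfy Inclusion 4, but it also lets more satisfy the temperature item of the septic-shock exclusion.

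**Working it through.** **Inputs.** The hypothermia pair is 36.0°C and 95.5°F (protocol Inclusion 4 and Exclusion 11; SAP 6.1.4.1, 6.1.4.6 and 9.2). The formulas are F = C × 9/5 + 32 and C = (F − 32) × 5/9.

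**The stated pair does not reproduce.**
- 36.0 × 9/5 + 32 = 96.8°F, against 95.5°F stated.
- (95.5 − 32) × 5/9 = 35.28°C, against 36.0°C stated.
- Gap: 96.8 − 95.5 = 1.3°F, or 36.0 − 35.28 = 0.72°C.

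Rounding does not explain it. Values from 35.95 to 36.05°C convert to 96.71 to 96.89°F, well away from 95.5.

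**The other pairs in version 2.0 do reproduce.**

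| Place | Stated pair | Converted |
|---|---|---|
| Fever bound, same line of Inclusion 4 | 38.0°C / 100.4°F | 100.4°F |
| Oral-switch criterion, section 14.3.1.2 | 37.8°C / 100°F | 100.04°F |
| PORT table, Appendix 2 ("Temperature < 35°C (95°F") | 35°C / 95°F | 95.0°F |
| PORT table, Appendix 2 | 40°C / 104°F | 104.0°F |

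Only the hypothermia pair fails.

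**It is not a PDF-reading fault.** The same numbers appear in version 1.0 and in every current copy. The version 2.0 change summary corrected the unit letter in synopsis Exclusion 11 from 95.5°C to 95.5°F and left the number alone.

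**Readings that fall between the two figures.** At 0.1° resolution these are seven Celsius readings, 35.3 to 35.9°C (95.54 to 96.62°F), or thirteen Fahrenheit readings, 95.5 to 96.7°F. All are below 36.0°C, and none is below 95.5°F.

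**When the result changes for such a subject.**
- Inclusion 4 needs at least two of four signs. It flips only when exactly one of the other three is present: 3 of the 2³ = 8 possible patterns.
- The septic-shock definition needs all six items. It flips only when the other five are all present: 1 of 2⁵ = 32 patterns.

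These counts show when the discrepancy matters. They are not frequencies.

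**The case against.** The strongest reply is that Celsius is plainly the working unit. It comes first, the Fahrenheit value is a bracketed gloss, and the SAP's SIRS, modified ATS and Table 8 rules use 36°C alone. On that view this is a conversion slip that matters only where a site screens in Fahrenheit, and the documents give neither the number of such sites nor the recording unit. Under SAP 6.2.2, CE membership is also determined by program plus a blinded manual review, so one threshold would probably be applied to everyone. For Exclusion 11, SAP 6.1.4.6 relies on what the investigator documented, so temperature is not tested again there.

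Much of this stands as a limit on the effect. It does not settle which figure governs. Both values are printed in an operative criterion, no section ranks them, and North America is among the regions named in the randomization strata, so Fahrenheit screening is a plausible assumption. The blinded review cannot apply a single rule until someone chooses it, and it cannot undo an eligibility decision already made at a site.

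**Conclusion.** The point holds and is minor. The pair is wrong by 0.72°C (1.3°F) in four protocol passages and three SAP passages, and nothing says which value controls.

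The reach is limited. The discrepancy can affect who is enrolled, but it reclassifies nobody already randomized, because the ITT population is everyone randomized. Neither the Early Clinical Response definition nor any sample-size or power figure uses temperature. The CE-PTE interval in this SAP is descriptive. The protocol makes CE a co-primary population for the EMA analysis, but that SAP is separate, and whether it repeats the criterion cannot be seen here.

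An actual effect requires a subject from 35.28°C up to just under 36.0°C with exactly one other Inclusion 4 sign, or with all five other septic-shock items and no need for the drug support that excludes by itself. It also requires the Fahrenheit figure to be used somewhere. The documents give no temperature distribution and no recording unit, so the number affected is unknown.

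**What to change.** The sponsor should reconcile the two values to one threshold with a matching conversion in all seven places: Inclusion 4 and Exclusion 11 in the synopsis and in sections 12.1 and 12.2, and SAP 6.1.4.1, 6.1.4.6 and 9.2. Which threshold is intended is for the sponsor to state. Sites should be told. The SAP should say that Inclusion 4 for the CE populations and the baseline hypothermia count are programmed from the recorded temperature converted to one unit, and that SAP 10.4 uses the same definition.

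The SAP side costs a wording correction and one line of unit conversion. The protocol side costs more than a notice: section 29.1 requires a written amendment with sponsor and ethics committee approval, and health authority approval where required, across up to about 150 sites. It could be bundled with any other amendment. No new data are needed.
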